This pivotal study was a prospective, multi-center, randomized, double-blinded placebo controlled dual-arm study of 100 subjects, of which 86 passed screening and were available for primary endpoint analysis. Subjects were adults with neck and shoulder pain of musculoskeletal origin (osteoarthritis, chronic muscle spasms and cervical and thoracic spine sprain strain) ongoing for at least 30 days with a recorded 0-100 VAS pain scale rating of 50 or greater. Average duration of neck and/or shoulder pain at study entry was about 6 years. Red laser light therapy was administered to the sagittal suture (top of head); left and right cervical, shoulder and torso areas; right and left shoulders during each of passive external rotation and passive adduction of the arm and shoulder; right and left cervical muscles and trapezius muscles during passive left lateral flexion of the cervical spine; and the right and left sternocleidomastoid and scalene muscles during passive range of motion, for a total of 13 minutes during a single treatment administration. Post-treatment follow-up period was 48 hours.

Primary efficacy success was evaluated immediately following the single device treatment administration relative to baseline as the change in neck and shoulder pain rating as recorded on the 0-100 VAS. Individual subject success was defined as a 30% or greater improvement (decrease) in the primary efficacy measure from baseline to endpoint. Study success was defined as a minimum 30% difference between treatment groups, comparing the proportion of individual successes. 65.1% of actively treated subjects attained individual success compared with 11.6% of control (placebo) subjects, resulting in a 53.5% difference between treatment groups, exceeding the 30% criteria by 23.5% ($p < 0.0001$). Hence the study met its primary efficacy endpoint. Additionally, the magnitude of the mean change in neck and shoulder pain VAS rating at endpoint relative to baseline was -29.02 for actively treated subjects and -4.91 for control (placebo) subjects, a 20.08 difference ($p < 0.0005$). No treatment-related adverse event was reported or observed for any subject throughout study duration, and no other safety issues occurred.

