2. The following Erchonia-sponsored clinical study outcome supported the 510(k) clearance for application of the simultaneous *combined Erchonia red and violet laser light therapy* to the *adjunctive temporary relief of minor chronic neck and shoulder pain of musculoskeletal origin*.

The study was a single (active treatment only) group non-inferiority design to evaluate equivalency or superiority of the Erchonia® EVRL in red/violet diode combination application with red diode only application in the temporary reduction of neck and shoulder pain of musculoskeletal origin. The comparative active data for the Erchonia® red diode only therapy was attained in the 2001 trial whose results successfully supported 510(k) clearance (K012580) of application of the PL3000 red diode only for the identical indication being sought through the results of this clinical trial.

Forty-four (44) subjects completed the study. Subjects were predominantly Caucasian (82%) males (39%) and females (61%) of average age 54.07 years with chronic neck and/or shoulder pain of musculoskeletal origin due to osteoarthritis, chronic muscle spasms or cervical and thoracic spine sprain strain who rated 50 or greater on the 0 to 100 Visual Analog Pain Scale (VAS). Average subject duration of neck and shoulder pain was 76.58 months with the location of pain evenly distributed across the right and left sides. Average VAS pain rating at study entry

was 65.00. In the 2001 comparative trial, 43 subjects received the active Erchonia® EVRL red diode only procedure administration.

Each subject received a single 13-minute active procedure administration with the Erchonia® EVRL at the investigator's test site as in the 2001 trial, differing only in dual-diode (red and violet) versus single-diode (red only) application, respectively.

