Study primary outcome measure was change in Visual Analog Scale (VAS) neck and shoulder pain rating from baseline to study endpoint evaluation. Individual subject success criteria was established as a 30% or greater decrease in VAS rating at endpoint relative to baseline. The study was pre-established as a non-inferiority study (equivalency or superiority) of the EVRL in red/violet diode combination therapy compared to the red diode only therapy as based upon the comparative data from the 2001 trial. Overall study success criteria was established as 65±5% of individual subject successes in the current trial. Seventy-five per cent (75%) of subjects in this dual diode violet/red laser study attained individual subject success compared with 65.1% of actively treated subjects in the 2001 trial, exceeding the overall study success criteria by 5%. The 29.80-point mean decrease (from 65.00 to 35.20) in neck and shoulder VAS pain rating from study Baseline to Endpoint for subjects in the violet/red laser study was comparable to (slightly above) the respective 29.02-point mean decrease (from 60.21 to 31.19) for the 2001 Active study subjects. As in the 2001 red laser only study, no adverse or other safety events were reported or recorded across study duration.

It was concluded that the application of simultaneous violet and red laser light was non-inferior to the application of red laser light alone in providing adjunctive temporary relief of minor chronic neck and shoulder pain of musculoskeletal origin.

3. The above two Erchonia-sponsored clinical trial outcomes, in addition to the below two Erchonia-sponsored clinical trial outcomes provided primary support for clearance of the indication for '*adjunctive use in providing temporary relief of nociceptive musculoskeletal pain*' for the respective light therapy devices:

➤ **CHRONIC LOW BACK PAIN:**

➤ **CHRONIC PLANTAR FASCIITIS HEEL PAIN:**

STUDY JUSTIFICATION

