Subjects will be males and females 22 years or older who present with chronic (30 consecutive days or longer) neck and/or shoulder pain diagnosed as being of musculoskeletal origin (osteoarthritis, chronic muscle spasm, cervical and thoracic spine sprain strain) and with a self-reported pain level of 50 or greater on the 0 to 100 VAS.

Sample Size

There will be 43 qualified subjects enrolled in this study.

Rationale for Sample Size

Sample size is determined to be identical to that of subjects enrolled in the active treatment group that forms the comparative data reference group in this study.

Recruitment

Subjects will be recruited from among:

- (i) The Principal Investigator's/test site's pool of existing and new patients
- (ii) Referrals from other suitable medical clinics and professionals
- (iii) Subjects who respond to the recruitment materials shown in **Appendix A**.

Compensation

A subject will not receive financial or any other form of compensation to participate in this clinical study. However, he or she will also not be charged for the cost of the study treatment with the Erchonia lasers or for the cost of any other directly-related evaluations or measurements that occur as a directly-associated part of his or her participation in the study.

STUDY PROCEDURE

STUDY TEST BATTERY

The following are the study measurement and assessment tools to be used and the variables to be recorded in this clinical study. At each evaluation point, the precise tools and variables that will be employed will be specified.

QUALIFICATION EVALUATION TOOL

PHYSICAL EXAMINATION

- (i) Inspection: Manipulation of the neck, shoulders, and cervical spine to evaluate for knots (muscle spasms), tightness, swelling, osteophytes, etc.
- (ii) Palpation Assessment: Physical assessment of the bony and soft tissues of the neck, shoulder, and cervical spine through touch with the pads of the fingers, to evaluate for muscle tightness and knotting, trigger points that cause pain and possibly also radiating pain.

BASELINE VARIABLES

NECK/SHOULDER PAIN VARIABLES

- (i) Location of pain: right side/left side/back of neck; right/left shoulder
- (ii) Duration of pain: months/years since onset of first episode of neck/shoulder pain

CONCOMITANT MEDICATION AND THERAPY USE

- (i) Over the counter and prescription medications currently used to relieve neck/shoulder pain, including duration, dosage, and frequency of use

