- Change in mean neck and shoulder pain VAS ratings across study duration: baseline, endpoint, 24 hours, and 48 hours post-procedure.
- Change in linear ROM measurements at study endpoint relative to baseline.
- Subject satisfaction with study outcome ratings across study duration.

INDIVIDUAL TEST SITES

Results will be presented by individual test site for comparison.

INDIVIDUAL SUBJECT RESULTS

Individual subject results for the primary study outcome measure will also be presented.

SAFETY ANALYSIS

Safety analysis will be based on all enrolled subjects and will be assessed by evaluating and comparing the frequency and incidence of observed and/or reported adverse events between subjects enrolled in the current study and subjects enrolled in the comparative reference study. A chi-square test with a continuity correction will be performed to compare the percentage of subjects who had adverse events between the two subject groups.

ADVERSE EVENTS

At each evaluation and measurement point throughout the clinical study, and at any other time throughout the duration of the clinical trial that is necessary, all potential adverse events reported by a subject or observed by an investigator will be recorded on the case report form, and subsequently evaluated by the investigator for its relation to the study procedure and whether any corrective action needs to be taken. All potential adverse events recorded will be appropriately reported to the governing IRB, as applicable.

It is unlikely and not expected that any adverse events will result from implementation of this clinical study protocol. Prior clinical trials evaluating application of Erchonia low level laser light, including numerous evaluating Erchonia lasers for the treatment of various pain conditions, including neck and shoulder nociceptive pain of musculoskeletal origin, have not typically yielded any adverse events or reactions.

ADVERSE EVENTS DEFINITION

An adverse event means any untoward medical occurrence associated with the use of an intervention in humans, whether or not considered intervention-related (21 CFR 312.32 (a)).

SERIOUS ADVERSE EVENTS (SAE) DEFINITION

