- **Definitely Related:** There is clear evidence to suggest a causal relationship, and other possible contributing factors can be ruled out. The clinical event occurs in a plausible time relationship to study capsule administration and cannot be explained by concurrent disease, medications, or other treatments.
- **Probably Related:** There is evidence to suggest a causal relationship, and the influence of other factors is unlikely. The clinical event occurs within a reasonable time after administration of the study capsule, is unlikely to be attributed to concurrent disease, medications, or other treatments.
- **Not Related:** The AE is completely independent of study capsule administration, and/or evidence exists that the event is definitely related to another etiology. The alternative, definitive etiology must be fully documented by the clinician.

C. Expectedness

The study investigator will be responsible for determining whether an AE is expected or unexpected.

An AE will be considered **unexpected** if the nature, severity, or frequency of the event is not consistent with the risk information previously described for the study intervention.

An AE will be considered **expected** if the nature, severity, or frequency of the event is consistent with the risk information previously described for the study intervention.

TIME PERIOD AND FREQUENCY FOR EVENT ASSESSMENT AND FOLLOW-UP

The occurrence of an AE or serious adverse event (SAE) may come to the attention of study personnel during study visits and interviews of a study subject presenting for medical care, or upon review by a study monitor.

An **unsolicited AE** is defined as one that is reported without specific prompting or in response to a general question.

A **solicited AE** is one that is specifically solicited through asking a question regarding a specific potential AE.

Reporting and data collection for an AE will distinguish if a captured AE was unsolicited or solicited.

AEs will be collected throughout study duration.

REASONABLY ANTICIPATED AND POTENTIAL ADVERSE EVENTS

SAEs are not anticipated to occur in this clinical study.

There are no anticipated adverse events in this clinical study.

Potential adverse events that may feasibly occur from application of the Erchonia® PPL laser device include, but are not necessarily limited to skin irritation, discoloring, rash, indentations, or infection.

ADVERSE EVENT RECORDING

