All AEs that occur, including local and systemic reactions, not meeting the criteria for SAEs will be captured on the appropriate AE case report form (CRF). Information to be collected includes event description, time of onset, clinician's assessment of severity, relationship to study product (assessed only by those with the training and authority to make a diagnosis), corrective action taken, time of resolution/stabilization of the event and if the subject was withdrawn from the study because of the AE. Recording will be done in a concise manner using standard, acceptable medical terms.

All AEs occurring while on study must be documented appropriately regardless of relationship. All AEs will be followed to adequate resolution.

Any medical condition that is present at the time that the subject is screened will be considered as baseline and not reported as an AE. However, if the study subject's condition deteriorates at any time during the study, it will be recorded as an AE.

Changes in the severity of an AE will be documented to allow an assessment of the duration of the event at each level of severity to be performed. AEs characterized as intermittent require documentation of onset and duration of each episode.

The study investigator will record all reportable events with start dates occurring any time after informed consent is obtained until 7 (for non-serious AEs) or 30 days (for SAEs) after the last day of study participation.

Events will be followed for outcome information until resolution or stabilization.

ADVERSE EVENT REPORTING

Adverse Event Reporting Timeframes

The table below lists the minimum AE reporting requirements for study Investigators. Reporting of all safety events to the Sponsor will be completed through Investigator submission of the AE CRF and any applicable supporting documentation

Table 1: Investigator AE Reporting Requirements

Type of AE	Report to	Reporting Timeframe (from time of learning of event)
Adverse Event (AE)	IRB	Per IRB reporting requirements
	Sponsor	Within 10 working days
Serious Adverse Event (SAE)	Sponsor	Within 24 hours
	IRB	Per IRB reporting requirements
Device Deficiency	Sponsor	Within 48 hours
	IRB	If SAE occurs due to the device deficiency, within 24 hours of learning of the event and per IRB reporting requirements
Device Related AE/SAE	Sponsor	Within 24 hours

Unanticipated Adverse Device Effect (UADE) Reporting

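### The planned chi-square on adverse events is undefined at the expected result (none in either study), has little power against moderate rates, and may not compare like with like.

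*Combined protocol and SAP*

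**What the plan says.** Safety Analysis bases the assessment on all enrolled subjects. It compares the frequency and incidence of adverse events between "subjects enrolled in the current study and subjects enrolled in the comparative reference study", and then adds: "A chi-square test with a continuity correction will be performed to compare the percentage of subjects who had adverse events". It gives no significance level, rule for zero events, confidence interval or detectable rate.

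The reference result is already known. Under Supporting Erchonia Corporation Clinical Data, item 2 says of the red/violet study, and expressly of the 2001 study too, that "no adverse or other safety events were reported or recorded across study duration". Item 1, on the red-laser study itself, reports no treatment-related adverse event in any subject and no other safety issue. It adds: "Post-treatment follow-up period was 48 hours".

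For the current study, Reasonably Anticipated and Potential Adverse Events states: "There are no anticipated adverse events in this clinical study". On timing, Adverse Event Recording has reportable events recorded from consent "until 7 (for non-serious AEs) or 30 days (for SAEs) after the last day of study participation". Time Period and Frequency for Event Assessment and Follow-up says only that events are collected for the duration of the study. Adverse Events Definition counts untoward events whether or not they are thought related.

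On size: "There will be 43 qualified subjects enrolled in this study", and item 2 says that in 2001 "43 subjects received the active" red-diode procedure.

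**The concern.** One row of the two-by-two table is reported as zero before enrolment begins, and the sponsor expects the other to be zero as well. A test that gives no value at the expected result is a poor choice for the only safety inference in a file meant to support a 510(k) submission.

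If a few events do occur, the test returns a p-value that will usually be non-significant at low or moderate true rates. Without a warning in the plan, a reader could take that as evidence of comparable safety. If an excess does appear, it could reflect a longer recording period or a wider event definition, and the plan gives no means of telling these apart from an effect of the added blue laser.

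**Working it through.** The plan states no power or detectable rate for this test, so there is no figure of its own to reproduce.

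**Inputs**
- Current study: n₁ = 43 (Sample Size).
- Reference: n₂ = 43, the 2001 active group (item 2; Rationale for Sample Size). Alternatives are 86 analysed or 100 enrolled (item 1), if the wording of Safety Analysis is read to include both arms.
- Reference events: 0 (items 1 and 2).
- Alpha: not given for this test. Two-sided 0.05 is assumed, the level given for the t-tests under Change Scores; 0.10 is shown as a variant.

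**1. Zero events in both groups.** For a table a, b / c, d with N = n₁ + n₂ and t events in total,

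χ² = N(|ad − bc| − N/2)² / [n₁ n₂ t (N − t)],

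with the correction not allowed to exceed the observed difference. At t = 0 the denominator is zero for any n₁ and n₂. The numerator is also zero, so the statistic is 0/0.

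**2. Events in the current study only.** With n₁ = n₂ = 43 and x events against 0, this reduces to χ² = 86(x − 1)² / [x(86 − x)].

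| x | Observed rate | χ² | p |
|---|---|---|---|
| 1 | 2.3% | 0 | 1.00 |
| 2 | 4.7% | 86 × 1 / (2 × 84) = 0.512 | 0.474 |
| 3 | 7.0% | 86 × 4 / (3 × 83) = 1.382 | 0.240 |
| 4 | 9.3% | 86 × 9 / (4 × 82) = 2.360 | 0.124 |
| 5 | 11.6% | 86 × 16 / (5 × 81) = 3.398 | 0.065 |
| 6 | 14.0% | 86 × 25 / (6 × 80) = 4.479 | 0.034 |

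The smallest observed count with p < 0.05 is therefore 6/43.

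**3. Power.** With the reference fixed at zero, power at a true rate π is P(X ≥ 6), where X is binomial (43, π).
- π = 5%: 2%
- π = 10%: 26%
- π = 14%: 57%
- π = 18%: 81%

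Power of 80% needs π of about 17.8%.

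**4. Sensitivity of the threshold**
- Alpha 0.10, reference 0/43: 5/43 (11.6%).
- Alpha 0.05, reference 0/86: 4/43 (9.3%, p = 0.020).
- Alpha 0.05, reference 0/100: 3/43 (7.0%, p = 0.042).

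**5. What zero events would show.** The exact two-sided 95% upper limit for 0/43 is 1 − 0.025^(1/43) = 0.082, or 8.2%.

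**6. Windows and definitions side by side**

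| | 2001 study | Current study |
|---|---|---|
| Follow-up | 48 hours after treatment | Scheduled assessments at endpoint, 24 and 48 hours |
| Event window | Not stated | Consent to 7 days (30 for serious events) after participation in one section; study duration in another |
| Events counted | None treatment-related (item 1); none at all (item 2) | All, related or not |

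**The case against.** Several points against this stand.

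- A reader might infer that the test cannot detect rates below 14%. The documents and the arithmetic do not support that. The 14% is the smallest observed rate that reaches p < 0.05, not a floor on the true rate: a true 10% still gives 26% power, and a true 14% only 57%. It also depends on an assumed alpha and comparator.
- A reader might infer that the 2001 event window was definitely shorter. The documents give the 2001 follow-up but not its event-collection window, and scheduled assessments in the current study also end at 48 hours. What they support is that the windows are unreconciled and probably differ.
- It is tempting to add that the chi-square approximation is invalid, since with fewer than 10 events in total the expected count in each group of 43 is below 5. That changes no decision here. Fisher's exact test gives p = 0.055 at 5/43 and 0.026 at 6/43, so the threshold is the same. Changing the test only yields p = 1 at zero against zero.
- The plan does report incidence, and it grades severity and relationship. It nowhere says that non-significance will be read as equal safety, and study success rests on VAS responders, not on this test.
- With no events, a report could simply say so.

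The last two points limit the consequences. They do not repair the method: the specified test yields nothing in the expected case, and the plan does not ask for the interval that would be informative there.

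**Conclusion.** The point holds and the safety analysis should be changed before the data are analysed; the primary efficacy conclusion is not affected. That the test is undefined at zero against zero rests on no assumption about alpha or denominator. The 14.0% threshold and the power figures assume two-sided alpha 0.05 and the 43 active reference subjects, which is the likelier reading. Across the alternatives shown, the threshold ranges from 7.0% to 14.0%.

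That the comparison may not be like for like is a possibility left open by the documents, not an established mismatch. It rests on the unstated 2001 window, on two descriptions of the current window, and on a 2001 zero that one summary ties to treatment-related events and the other extends to all events.

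**What to change.** 1. Make the main safety result the incidence of subjects with any adverse event, and with a device-related adverse event, in the current study, each with an exact (Clopper-Pearson) 95% confidence interval. Use subjects who received treatment, because untreated enrolled subjects would dilute the rate. Also show all enrolled subjects, as Safety Analysis now specifies.
2. Reconcile Adverse Event Recording with Time Period and Frequency for Event Assessment and Follow-up, and state which window feeds the safety tables.
3. If the 2001 comparison is kept, name the reference group. Limit it to events within 48 hours of treatment and to the same event definition in both studies. Give an exact confidence interval for the difference, label it descriptive, and state that non-significance is not evidence of equal safety.

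Cost: SAP wording, with no new data from current subjects, since events are already assessed at endpoint, 24 and 48 hours and time of onset is recorded. Keeping item 3 requires the sponsor to confirm the 2001 window and definition from its own records. The downside for the sponsor is that, with no events in 43 treated subjects, the report shows an upper limit near 8% in place of a non-significant p-value.
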